8. STUDY PROCEDURES

The study schedule of events and the specific procedures performed at each visit are shown in Table 1, Schedule of Events. Each patient will undergo a total of 11 visits, including an initial/screening visit, the procedure visit, and 9 post-operative visits. The Month 1 post-operative visit may be a telephone visit or a clinic visit. More visits may be required when medically necessary.

Table 1: Schedule of Study Events

Procedures	Screening	Procedure Date	W 1ª	M 1 ^b	M 3, 6 & 12 d	M 24, 36, 48, 60 ^e or Withdrawal
Informed Consent	Х					
Inclusion/Exclusion	Х					
Demographics	Х					
Targeted Medical History	х					
ECOG & Karnofsky	Х		Х	Χ°	Х	Х
Pertinent Medication	Х		Х	Х		
Discontinue anticoagulation, as clinically indicated	х					
CT/MRI Scan ^f	Х		Χg		Х	Х
Record tumor characteristics	х					
Chest X-Ray			Χg			
Cryoablation procedure		Х				
Labs h	Х					
Quality of Life (SF-12) i	Х			X	Х	х
Safety Assessments		Х	Х	Х	Х	Х

^aWeek 1 visit within +/- 7 days of cryoablation procedure

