8.4. Month 1 - Follow-up (Telephone Interview or Clinic Visit)

Patients may be contacted by telephone or return 1 Month (+21/-7 days) post cryoablation procedure to complete the following assessments:

- Quality of Life assessments (SF-12);
- ECOG (Clinic Visit Only);
- Karnofsky Performance Scale (Clinic Visit Only);
- Safety assessments;
- Assess any new cancer treatment(s);
- Current pertinent concomitant medication.

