8.5. Months 3, 6 and 12 - Follow-up

Patients will return 3, 6 and 12 Months (+/-45 days) post cryoablation procedure to complete the following assessments:

- ECOG:
- Karnofsky Performance Scale;
- Quality of Life assessments (SF-12);
- CT/MRI Scan, with contrast;
- Safety assessments;
- Assessment of disease progression, including retreatment;
- Assess any new cancer treatment(s).

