8.6. Months 24, 36, 48, 60 and Study Completion or Withdrawal

Patients will return 24, 36, 48 and 60 months (+/- 90 days) post cryoablation procedure or at Study Withdrawal and complete the following assessments:

- ECOG;
- Karnofsky Performance Scale;
- Quality of Life assessments (SF-12);
- CT/MRI Scan, with contrast:
- Safety assessments;
- Assessment of disease progression, including retreatment;
- Assess any new cancer treatment(s).

Patients who request Early Termination from the study will be asked to return for a final visit to complete the above assessments.

Patients may be considered "lost to follow-up" after 3 unsuccessful attempts to contact the patient with on contact being a registered letter to the last known address of the patient. Site should document all attempts to contact the patient in the source documents.

CUC10-LNG06-04 Page 16 of 38

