9.6. Computed Tomography (CT) and Magnetic Resonance Imaging (MRI)

As outlined in this protocol, all patients will have an initial CT or MRI prior to therapy. The cryoablation procedure will be completed under CT guidance only. Follow-up imaging at Week 1 will be either CT, MRI or X-Ray. At Months 3, 6, 12, 24, 36, 48 and 60, follow up imaging will be CT or MRI with contrast unless contrast is contraindicated.

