11.5.4. Other Endpoints

Technically successful treatment definition

A technically successful treatment will be defined by an ablation volume encompassing the tumor with at least a 5 mm margin.

Technical success will be calculated on a per tumor level as well as a patient level. To be considered a technical success on a patient level all tumors treated during the baseline procedure must meet the technical success criteria.

Disease recurrence or progression definitions

Disease recurrence or progression will be determined locally by evidence of an increase in tumor size and/or contrast enhancement.

Disease-specific survival rate is defined as the time in days from cryoablation procedure to death due to lung cancer. Patients who are alive will be censored at the date of their last visit. Patients who have died from causes other than lung cancer will be censored at the time of death. Disease-specific survival rates will be summarized by using Kaplan-Meier methodology.

Overall survival rate is defined as the time in days from cryoablation procedure to death. Patients who are alive will be censored at the date of the last visit. Overall survival rates will be summarized by using Kaplan-Meier methodology.

Time to recurrence is defined as the time in days from cryoablation procedure to disease recurrence or progression. Patients without disease recurrence or progression will be censored at the date of their last visit or their date of death (due to any cause). Recurrence free survival rates will be summarized by using Kaplan-Meier methodology.

Intra-procedural data

Initial cryoablation procedure information including the type of procedure, tumor size and number, cryoablation needle type and the number of each type of needle used, freeze and thaw times, method of thaw (active or passive), and ice formation and how it encompasses the tumor will be summarized.

Physical performance and quality of life

Physical performance (ECOG and KPS) and quality of life (SF-12) assessments will be made by examining the change in the baseline scores to those reported post-operatively as defined in Sections 9.3.1 and 9.5, respectively.

CUC10-LNG06-04 Page 20 of 38

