#### Disease recurrence or progression

Disease specific survival, overall survival, and time to disease recurrence or progression will be analyzed by Kaplan-Meier methodology. These measures are defined as:

**Disease-specific survival** will be analyzed as the time in days from cryoablation procedure to death due to lung cancer. Patients who are alive will be censored at the date of their last visit. Patients who have died from causes other than lung cancer will be censored at the time of death.

**Overall survival** will be analyzed as the time in days from cryoablation procedure to death. Patients who are alive will be censored at the date of the last visit.

Freedom from disease recurrence or progression will be analyzed as the time in days from cryoablation procedure to disease recurrence or progression, determined locally by evidence of an increase in tumor size and/or contrast enhancement. Patients without disease recurrence or progression will be censored at the date of their last visit or their date of death (due to any cause).

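### Freedom from recurrence is censored at last visit or death rather than at the last assessable scan, so the curve can read too high if death follows undetected progression or scans are missed

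*SAP*

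**What the plan says.** The SAP, under Disease recurrence or progression, defines the event as recurrence or progression "determined locally by evidence of an increase in tumor size and/or contrast enhancement". Patients without it "will be censored at the date of their last visit or their date of death (due to any cause". Protocol 11.5.4 uses the same rule and adds: "Recurrence free survival rates will be summarized by using Kaplan-Meier methodology". Neither document ties censoring to the last scan.

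The imaging schedule is in Protocol 9.6: "At Months 3, 6, 12, 24, 36, 48 and 60, follow up imaging will be CT or MRI with contrast unless contrast is contraindicated". The windows are in Protocol 8.5 ("Patients will return 3, 6 and 12 Months (+/-45 days) post cryoablation procedure") and 8.6 ("Patients will return 24, 36, 48 and 60 months (+/- 90 days) post cryoablation procedure or at Study Withdrawal"). CT/MRI is listed at each of these visits, including withdrawal.

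Some contacts have no required CT/MRI. For Month 1, Protocol 8.4 says: "Patients may be contacted by telephone or return 1 Month (+21/-7 days) post cryoablation procedure". Section 8 adds: "More visits may be required when medically necessary". Protocol 11.3 and the SAP's Handling of Missing Data give no rule for a missed scan or for a death before the next scan, and no sensitivity analysis.

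**The concern.** Both signs of the event, growth and enhancement, are seen only on imaging. A patient who progresses after one scan and dies before the next has no recorded event and is censored at death. Kaplan-Meier then assumes that this patient had the same future risk of recurrence as those still followed. In Stage 4 disease the assumption is doubtful, because patients who die between scans may be the ones who had progressed. That link is clinically plausible, but it is an inference: the documents give no figure for it.

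Time to recurrence is a named endpoint (Protocol 5.3), and Protocol 11.2 and the SAP's Sample Size Justification say that this study's estimates will power the pivotal study. An optimistic recurrence rate would leave that study short of events, and a confidence interval would not reveal the bias. The Protocol's label for the curve hides it further, since a reader would expect deaths to count as events.

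**Working it through.** The documents state no rate, event count or power for this endpoint, so there is no figure to reproduce.

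**1. Who is affected.** For a living patient who keeps the schedule from Month 3, the last visit is also the last scan. The dates differ only after a Month 1 or unscheduled contact without imaging, or a missed scan. The main exposure is death between scans.

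**2. How long the gap can be.** After Month 12, scans are 12 months apart. One scan 90 days early and the next 90 days late give 12 months + 180 days, about 18 months, and more if a scan is missed.

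**3. Model (assumed inputs).** Recurrence hazard per month λ = −ln(S12)/12, where S12 is 12-month freedom from recurrence. Death hazard before recurrence μ = −ln(annual survival)/12, multiplied by a hazard ratio (HR) after recurrence. True freedom from recurrence at month t is S12^(t/12). Recurrence is recorded only at a scan, and scans are spread uniformly over the protocol windows. Curves are read after the Month 12, 24 and 36 windows close and compared with the truth at the nominal month.

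**4. First set of scenarios.** S12 is 70% or 50%. Annual survival before recurrence is 89.4% (the one-year figure of the 20-patient series in Protocol 3.2) or 75% (assumed). There were 400,000 simulated patients per scenario. Error in percentage points:

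| HR | Missed scans | Rule as written | Last-scan censoring |
|---|---|---|---|
| 1 | 0% | 0 to +0.2 | −4.8 to −1.0 |
| 2 | 0% | +0.6 to +4.1 | −2.7 to −0.6 |
| 2 | 10% | +2.0 to +6.1 | −1.4 to +1.1 |
| 4 | 0% | +1.6 to +11.3 | −0.4 to +4.3 |
| 4 | 10% | +3.2 to +13.9 | +0.7 to +5.4 |

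For HR 2 and 4, repeat runs moved the ends of these ranges by at most 0.2 points.

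**5. Second set, with different inputs.** 12-month progression is 35% (the share of patients with local recurrence in the same series), annual survival before progression 92% and loss to follow-up 0.4% per month; the last two are assumed. At HR 3 this gives an overall one-year survival of 89.3%, close to the series' 89.4%. True 36-month freedom from progression is 0.65³ = 27.5%. Estimates at 36 months with 0 / 10 / 20% missed scans:

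| HR | Rule as written | Last-scan censoring | Death as an event |
|---|---|---|---|
| 1 | 26.7 / 28.6 / 30.8% | 25.3 / 26.7 / 28.1% | 20.2 / 21.7 / 23.3% |
| 3 | 28.9 / 30.9 / 33.4% | 26.9 / 28.1 / 29.4% | 20.1 / 21.3 / 22.8% |
| 6 | 32.0 / 34.6 / 37.1% | 29.2 / 30.6 / 31.6% | 20.0 / 21.0 / 22.0% |

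At HR 3 the rule as written is 28.9 − 27.5 = 1.4 to 33.4 − 27.5 = 5.9 points too high. Between 6.6% and 9.2% of patients progress and die before any scan shows it, and all are censored as recurrence-free. At HR 1 the rule reads high only when scans are missed: 28.6 − 27.5 = 1.1 and 30.8 − 27.5 = 3.3 points.

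**6. The death-as-event curve has its own target.** That target is 0.65³ × 0.92³ = 0.2746 × 0.7787 = 21.4%. The last column runs from 20.0 − 21.4 = −1.4 to 23.3 − 21.4 = +1.9 points around it, and it hardly moves with the hazard ratio.

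**The case against.** A reader might infer two stronger things.

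The first is that unscanned time itself is credited as recurrence-free: a patient scanned at Month 12 who dies at Month 22 would gain ten months. Kaplan-Meier does not work that way. A patient in the risk set affects the estimate only when someone has an event, and in this model events occur only at scans. With every scan exactly on schedule and none missed, the written rule and last-scan censoring give the same curve. At HR 6 in the second set both read 32.6% against a true 27.5%. The bias comes from treating death after undetected progression as uninformative. The two rules separate only through the spread of the windows and missed scans.

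The second is that the error is always favourable. It is not. With HR 1 and no missed scans the rule as written is within 0.2 points of the truth in the first set and slightly low in the second (26.7% against 27.5%).

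Other objections stand in part:

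- Last-scan censoring has a bias of its own, because it removes event-free patients at a scan on account of their later death. At HR 2 without missed scans the two rules err by similar amounts in opposite directions.
- The model allows detection only at scheduled scans, whereas the Protocol permits extra visits. If half of progressed patients were scanned two months before death (an assumption), then at HR 2 without missed scans the written rule errs by +0.3 to +1.3 points and last-scan censoring by −3.8 to −0.7, so the written rule is closer. At HR 4 last-scan censoring remains closer.
- The 10% and 20% missed-scan rates have no source in the documents.
- Sampling error is larger than these biases. Exact 95% intervals are 47.2% to 82.7% for 20 of 30 and 48.3% to 79.4% for 26 of 40, with half-widths of about 18 and 16 points.
- The main efficacy endpoint is a visit-based proportion and does not use this rule.

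**Conclusion.** The point holds conditionally. The curve reads too high if death is more likely after undetected progression, or if scans are missed. The size is about +0.5 to +4 points at HR 2 with no missed scans and up to about +14 at HR 4 with 10% missed. With neither condition the rule is essentially unbiased. The documents supply no hazard ratio and no missed-scan rate, so these are ranges under assumptions and not predictions for this trial.

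Last-scan censoring is a partial remedy. Its worst error in the first set is about 5 points in either direction, against about 14 for the written rule, and with missed scans and HR 2 or more it is the closer of the two. It does not remove the bias from informative death.

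Severity is modest. The endpoint is supportive and descriptive, without hypothesis testing, in 30 to 40 patients. The reason to act is the planned use of the estimates for the pivotal study.

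**What to change.** In the SAP (Disease recurrence or progression) and Protocol 11.5.4:

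1. Censor patients without recurrence or progression, including those who later die, at the date of their last CT/MRI on which the treated tumors could be assessed. Censor patients with no such scan after the procedure at Day 1.
2. Report the present rule beside it, so that the gap between the two curves shows the sensitivity.
3. Also report a curve that counts death as an event, which is what the Protocol's label implies, or a cumulative incidence of recurrence with death as a competing risk. Name each curve for what it estimates.

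The cost is a few sentences in each document and one or two extra displays, using dates of scans already required. The downside is that the last-scan curve would read about 1 to 5 points low if deaths were truly unrelated to recurrence and no scan were missed. Keeping the present rule alongside makes that visible.

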#### Intra-procedural data

Initial cryoablation procedure information will be summarized by descriptive statistics. These include but may not be limited to:

- Type of procedure
- Tumor size and number
- Cryoablation needle type
- Number of each type of needle used
- Freeze and thaw times
- Ice formation
- How ice formation encompasses the tumor
- Who performed the procedure
- Cryoablation system used
- Cryoablation completion
- Antibiotic administration
- Type of anesthesia used
- Procedure duration
- Location, reason, and duration of chest tube placement

# Physical performance and quality of life

Physical performance and quality of life assessments will be made by examining the change in the baseline scores to those reported post-operatively. Physical function assessments will be measured using Eastern Cooperative Oncology Group (ECOG) and Karnofsky Performance Scale

Confidential Page 5 of 9

### Galil Medical – ECLIPSE Statistical Analysis Plan - Version 2.0 (Aug. 27, 2012)

(KPS), and will be measured at screening, Week 1 and Months 3, 6, 12, 24, 36, 48 and 60. Quality of life will be measured by the Short Form (SF)-12 generic measure at screening, Months 1, 3, 6, 12, 24, 36, 48 and 60. The ECOG scale, KPS scale and each of the eight SF-12 domains will be summarized at each time point by descriptive statistics. Percent change from baseline for each measure will also be summarized by descriptive statistics.

Confidential Page 6 of 9

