5.3. Other Endpoints

Other endpoints for this study include, but are not limited to:

- Assessing overall disease specific survival at 3, 6, 12, 24, 36, 48 and 60 months post cryoablation.
- Assessing time to disease recurrence or progression.
- Assessing the changes in physical function and quality of life over time. (See Section 11.5.4)
- Assessing cryoablation technical success. (See Section 11.5.4)

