7.2. Inclusion Criteria

Eligible patients for this study must meet all of the following criteria:

- 7.2.1. Patient must be at least 18 years old.
- 7.2.2. Patient has signed a written informed consent.
- 7.2.3. Patient presents with Stage 4 pulmonary metastatic disease with metastatic disease previously confirmed by prior biopsy; or
 Patient presents with Stage 4 pulmonary metastatic disease previously confirmed on
 - Patient presents with Stage 4 pulmonary metastatic disease previously confirmed on imaging (e.g. CT or MRI) with known (biopsied) primary disease.
- 7.2.4. Patient has up to 3 local metastases unilaterally targeted by cryoablation. (treatment in both lungs must be on separate treatment days) Maximum number of pulmonary tumors bilaterally per patient will be 5 total pulmonary tumors.
- 7.2.5. Targeted tumor(s) defined as intra pulmonary or pleural with a maximum size of 3.5 cm.
- 7.2.6. The target tumor is determined (by CT/MRI images) to be in a location where cryoablation is technically achievable based on the proximity of adjacent organs and structures.
- 7.2.7. ECOG performance status of 0-2.
- 7.2.8. Karnofsky Performance Scale (KPS) score ≥60.
- 7.2.9. Platelet count >50,000/mm³ within 60 days prior to study treatment.
- 7.2.10. INR < 1.5 within 60 days prior to study treatment.
- 7.2.11. Patient has a life expectancy of >3 months.
- 7.2.12. Patient is clinically suitable for cryoablation procedure.

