25. APPENDIX C: PERFORMANCE STATUS SCORING (ECOG)

Grade	ECOG
0	Fully active, able to carry on all pre-disease performance without restriction
1	Restricted in physically strenuous activity but ambulatory and able to carry out work of a light or sedentary nature, e.g., light house work, office work
2	Ambulatory and capable of all self-care but unable to carry out any work activities. Up and about more than 50% of waking hours
3	Capable of only limited self-care, confined to bed or chair more than 50% of waking hours
4	Completely disabled. Cannot carry on any self-care. Totally confined to bed or chair
5	Dead

CUC10-LNG06-04 Page 34 of 38

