# **General Analysis Methods**

Data will be analyzed using descriptive statistics. Continuous variables (e.g., age) will be summarized by the number of patients, mean, standard deviation, median, interquartile range, minimum and maximum. Categorical variables (e.g., race) will be summarized by frequencies and percentages of patients in each category.

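### Percent change from baseline cannot be computed for ECOG in patients who enter at grade 0, and it weights grades 1 and 2 unequally, so this one summary can mislead

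*SAP*

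**What the plan says.** Protocol 5.3 lists this among the other endpoints: "Assessing the changes in physical function and quality of life over time". Physical function is measured by ECOG and KPS.

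The SAP section Physical performance and quality of life contains three relevant statements:

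- a general aim: "Physical performance and quality of life assessments will be made by examining the change in the baseline scores to those reported post-operatively";
- a summary by visit: "The ECOG scale, KPS scale and each of the eight SF-12 domains will be summarized at each time point by descriptive statistics";
- a change statistic: "Percent change from baseline for each measure will also be summarized by descriptive statistics".

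The general aim names no statistic. Protocol 11.5.4 has similar wording and does not mention percent change. Under General Analysis Methods, continuous variables "will be summarized by the number of patients, mean, standard deviation, median, interquartile range, minimum and maximum".

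Inclusion criterion 7.2.7 in the protocol reads "ECOG performance status of 0-2". Appendix C gives the number 0 to the best grade: "Fully active, able to carry on all pre-disease performance without restriction". Neither document exempts ECOG from the percent-change summary or gives a rule for a baseline of zero. The missing-data sections do not cover it either.

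**The concern.** The percent-change sentence follows directly on the one that lists the measures, so it includes ECOG. Two problems follow.

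First, the statistic does not exist for a patient whose baseline grade is 0. With no rule in the SAP, the likely default is a missing value, and the patient is then absent from the column. The omission is selective, because a patient at grade 0 can only stay the same or worsen.

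Second, among patients at grades 1 and 2 the size of a one-grade change depends only on the starting grade.

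The mean percent change in ECOG can therefore differ from the average movement of the patients in size and even in sign. A reader looking for decline in performance status after cryoablation could not see it in this column for the patients who started out fully active. Percent change is also the only change-from-baseline statistic that the SAP names for this endpoint.

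**Working it through.** The plan gives no figure on this point, so there is none to reproduce.

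**Inputs.** Baseline ECOG is 0, 1 or 2 (Protocol 7.2.7). The planned sample is 30 to 40 patients (Protocol 5; SAP, Study Design). The share entering at grade 0 is not given. Every mix and transition below is an assumption, with all 40 patients observed.

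**Formula.** Percent change = 100 × (follow-up − baseline) / baseline. A positive value means worse.

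| Baseline | One grade better | No change | One grade worse |
|---|---|---|---|
| 0 | not possible | undefined (0/0) | undefined (1/0) |
| 1 | −100% | 0% | +100% |
| 2 | −50% | 0% | +50% |

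**Share without a value.** This equals the share entering at grade 0. If that share is 20% to 80%, then 6 to 24 of 30 patients, or 8 to 32 of 40, have no percent change.

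**Examples.** Mean percent change is taken over patients with baseline above 0, and mean absolute change over all 40. Mixes are counts at grades 0/1/2.

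1. *Sign reversed.* Half of the grade 0 patients go to 1, and a fifth to a quarter of the grade 1 patients go to 0.
   - 10/20/10 (five worsen, four improve): (4 × −100)/30 = −13.3%, against (5 − 4)/40 = +0.025 grade.
   - 20/15/5 (ten worsen, three improve): (3 × −100)/20 = −15%, against (10 − 3)/40 = +0.175 grade.
   - 30/8/2 (fifteen worsen, two improve): (2 × −100)/10 = −20%, against (15 − 2)/40 = +0.325 grade.

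   In the 20/15/5 case the mean by visit still shows the worsening: 25/40 = 0.625 at baseline and 32/40 = 0.80 at follow-up.

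2. *Opposite error, 20/15/5.* Five of the fifteen grade 1 patients go to 2, and all five grade 2 patients go to 1: (5 × 100 + 5 × −50)/20 = +12.5%, against (5 − 5)/40 = 0 grade.

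3. *Right sign, grade 0 patients not visible, 20/15/5.* Five go from 1 to 2 and two from 2 to 3: (5 × 100 + 2 × 50)/20 = +30%. The figure is the same whether none or ten of the grade 0 patients also worsen by one grade. The mean absolute change is 7/40 = +0.175 in the first case and 17/40 = +0.425 in the second.

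The median percent change is 0 in all of these examples, since at least half of the defined values are zero and neither tail reaches the middle.

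**The case against.** The strongest reply is that the endpoint does not rest on this column.

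- **KPS covers the same patients.** Eligibility requires KPS of at least 60, so KPS percent change is defined for every eligible patient, including those at ECOG 0. This stands and limits the harm. It does not repair the ECOG column.
- **Plain change is already planned.** Protocol 11.5.4 says that "quality of life (SF-12) assessments will be made by examining the change in the baseline scores to those reported post-operatively", and the SAP's general statement agrees, so percent change can be read as an extra. This stands in part: the intention is there, but no absolute-change statistic or table is specified.
- **The visit summaries and n would show the problem.** They would show the overall level and the reduced denominator. But a mean level at each visit is not within-patient change, and over 60 months of follow-up in Stage 4 disease the patients seen at a visit may differ from those at baseline.
- **Any percent change depends on baseline.** A 10-point KPS drop is −16.7% from 60 and −10.0% from 100. Uneven weighting is therefore not peculiar to ECOG, though it is coarser there (100% against 50%). The undefined value at zero is the firmer part of the point. Mean absolute grade change also treats an ordinal scale as evenly spaced, which is a reason to add a shift table.
- **The examples are chosen.** They are. The first needs half of the grade 0 patients to worsen while the only movement at grade 1 is improvement. The second needs every grade 2 patient to improve. The medians do not move. The examples show what can happen and do not forecast what will.

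**Conclusion.** The concern holds, as a minor one. For a patient entering at ECOG 0 the specified statistic cannot be calculated. That follows from the eligibility rule and the coding of the scale and needs no assumption about the data. The size does depend on assumptions: in the mixes used, 25%, 50% or 75% of patients have no value, and the mean percent change can take the wrong sign, show a change where there is no net change, or have the right sign while missing any decline in the grade 0 patients. There is no constant direction of error.

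The consequence is limited to one supportive summary in a descriptive study without hypothesis tests, with ECOG by visit and the KPS summaries still available. The statement that grade 0 patients drop out assumes that undefined values are left missing. Another ad hoc choice, such as entering 0%, would give different results, and the SAP does not choose.

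**What to change.** In the SAP, exempt ECOG from the percent-change sentence. For ECOG, specify instead:

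- absolute change in grade from baseline at each visit; and
- a shift table of baseline grade by grade at each visit, with the numbers improved, unchanged and worsened by at least one grade, and the denominator at each visit.

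Keep the planned ECOG summary at each visit. No change to KPS or SF-12 is needed for this point. The new summaries include every patient with both a baseline and a follow-up grade and agree with Protocol 11.5.4. The cost is one SAP sentence and one table shell, with no new data.
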